6.3.5 Best Overall Response

The best overall response is the best response recorded from the start of the treatment until disease progression/recurrence (taking as reference for progressive disease the smallest measurements recorded since the treatment started). The patient's best response assignment will depend on the achievement of both measurement and confirmation criteria.

6.3.6 Duration of Response

The duration of response (DOR) is measured from the time measurement criteria are met for CR or PR (whichever is recorded first) until the first date that recurrent or progressive disease is objectively documented (taking as reference for progressive disease the smallest measurements recorded since the treatment started), death, or, in the absence of PD, date of last assessment.

6.3.7 Progression-Free Survival

Progression-free survival (PFS) is defined as the duration of time from the date of study enrollment until time of disease relapse, disease progression, or death, whichever occurs first.

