3.5 POST-TREATMENT EVALUATIONS

Post-treatment evaluations (i.e., End of Treatment Visit) will be performed approximately 30 days after the last dose of protocol treatment in all subjects. If a subject initiates a new anti-cancer therapy within 30 days after the last dose of trial treatment, the 30-day safety follow-up visit must occur before the first dose of the new therapy. If the patient cannot return to the Clinical Center for this visit, a request will be made to have a local physician or laboratory collect a CBC with differential and send the results. If this is not possible, patients may be assessed by telephone for symptoms.

Unless otherwise noted for subjects who come off treatment without evidence of disease progression, follow-up will occur at the following time point: every 60 days (\pm 7 days) for 6 months; then every 90 days (\pm 14 days) for 2 years; then every six months (\pm 28 days) for 2 years, then annually (\pm 6 weeks) at the discretion of the investigator. See Section [3.5.3](#). Any other evaluations and tests should be performed as clinically indicated.

Upon disease progression or initiation of other anti-cancer therapy, contact will be for survival only (i.e., every 3 months [\pm 4 weeks]) until the subject is off study; unless otherwise clinically indicated. See Section [3.5.4](#) and the Study Calendar (Section [3.6](#)) for additional information. Any adverse events which are present at the time of discontinuation should be followed in accordance with the safety requirements.

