3.5.3 Follow-Up Visits- Prior to Disease Progression

Patients who complete trial treatment without evidence of disease progression will move into the Follow-up Phase and may be assessed every 60 days (\pm 7 days) for 6 months; then every 90 days (\pm 14 days) for 2 years; then every six months (\pm 28 days) for 2 years, then annually (\pm 6 weeks) after finishing treatment by radiologic imaging or other clinical assessments to monitor disease status. Imaging assessment will be performed at each scheduled post-treatment follow-up visit for up to 3 years. Every effort should be made to collect information regarding disease status until the start of new anti-neoplastic therapy, disease progression, death, or end of the study. If the patient cannot return to the Clinical Center for any of these visits, a request will be made to have a local physician or laboratory collect a CBC with differential and send the results. If this is not possible, patients may be assessed by telephone or email for symptoms.

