6.3.3 Response Criteria for CTCL

Global Response (GR) score (**APPENDIX C**) will be used for assessing response in patients with CTCL (53). GR score incorporates separate responses in each component of the TNBM staging (i.e., skin, nodes, viscera and blood; **APPENDIX C**). No patient with a global OR should have less than a PR in the skin.

The mSWAT (11) is an instrument utilized to track the skin tumor burden in MF/SS. It measures the percentage total body-surface area (TBSA, %) involvement separately for patches, plaques, and tumors within 12 body regions using the patient's palm and fingers representing 1% of TBSA. Patients with erythroderma are assessed for percentage of TBSA involved with patches and/or plaques. The percentage of TBSA for each lesion type is multiplied by a number (patch = 1, plaque = 2; tumor = 4) and summed to derive the mSWAT score. The mSWAT for each patient will be determined by the same individual at all study visits.

A complete response (CR) requires 100% clearing of skin disease and a partial response (PR) requires $\geq 50\%$ reduction in the mSWAT score compared with baseline. CR/PR requires confirmation by repeat assessment after ≥ 4 weeks. Stable disease is defined as less than 50% reduction to less than 25% increase in the mSWAT score compared with baseline. PD is defined as $\geq 25\%$ increase in the mSWAT score from baseline or $\geq 50\%$ increase in the sum of the products of the greatest diameters of pathologically positive lymph nodes compared with baseline.

Time to response is the time from the first treatment dose until the patient first meets the criteria for a 50% decrease in the GR score. The duration of response (DOR) is the time from first CR/PR until the GR score is increased from nadir to more than 50% of the difference between the baseline and nadir scores. Time to progression (TTP) is the time from start of treatment until PD. If patients goes off treatment for any purpose, this date is used for determination of TTP and/or DOR.

As “skin flares” have been described in patients with SS receiving the anti-PD-1 antibody Pembrolizumab (18), patients with SS whose only sign of PD is an increase in mSWAT score (i.e., who have normal/decreasing number of circulating Sézary cells) will continue treatment and be re-evaluated in 2-4 weeks to confirm disease progression. Patients whose PD is not confirmed on re-evaluation will be noted to have had a skin flare

Table 15: Calculating mSWAT Score

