6.3.9 Event-Free Survival

Event-free survival (EFS) is defined as the duration of time from the date of study enrollment until time of disease relapse, disease progression, alternative therapy for lymphoma given (such as radiation), or death, whichever occurs first.

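### Disease assessment stops at new anti-cancer therapy, but PFS has no rule for a switch before progression, and the two DOR rules do not agree

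*Combined protocol and SAP*

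**What the plan says.** - **Follow-up.** Section 3.5: "Upon disease progression or initiation of other anti-cancer therapy, contact will be for survival only", with an exception only where clinically indicated. Section 3.5.3 seeks disease status "until the start of new anti-neoplastic therapy, disease progression, death, or end of the study". Section 3.5.4 then moves the patient to survival follow-up, which records new treatments and vital status. Footnote 6 of the study calendar (3.6) agrees.
- **PFS (6.3.7).** Time from enrollment "until time of disease relapse, disease progression, or death, whichever occurs first". New therapy is not mentioned, and no censoring date is given.
- **DOR (6.3.6).** It ends at documented recurrence or progression, "death, or, in the absence of PD, date of last assessment".
- **TTP and DOR in CTCL (6.3.3).** "If patients goes off treatment for any purpose, this date is used for determination of TTP and/or DOR".
- **EFS (6.3.9).** Its events include "alternative therapy for lymphoma given (such as radiation), or death, whichever occurs first".
- **Analysis.** Sections 10.4.1 and 10.4.3 specify Kaplan-Meier curves and confidence intervals, with no censoring conventions. Section 10.4.7 repeats all secondary endpoints by diagnosis and PD-L1 level.
- **Missed visits (3.5.3).** A patient who cannot return may have a local CBC. Failing that: "If this is not possible, patients may be assessed by telephone or email for symptoms".

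**The concern.** PFS needs progression to be looked for until the event or the censoring date. Here the scheduled looking stops at the switch, but the definition does not. In a patient who switches before progression, the next event likely to be recorded is death, under a treatment that is not being studied.

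Such switches are foreseeable. Treatment ends after six cycles at most (3.1, 3.8.1). Patients also leave it for late DLT-type toxicity (3.1.1.2), for holds beyond six weeks (3.3, 3.8.1) or for a need for prohibited therapy (4.2). All of these can leave a patient with relapsed or refractory lymphoma off treatment without progression and free to start something else. EFS names alternative therapy, so the authors had switching in mind but gave PFS no matching rule.

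At stake are PFS and DOR, both listed secondary endpoints in 10.1. With at most 30 patients split by diagnosis and PD-L1 level, one or two switchers can visibly move a curve, and a rule chosen after the data are seen is hard to defend.

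**Working it through.** **1. What the text gives for each kind of patient who switches without progression**

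| Patient | PFS (6.3.7) | DOR (6.3.6) | DOR in CTCL (6.3.3) | EFS (6.3.9) |
|---|---|---|---|---|
| Later dies | Event at death | Death or last assessment; not stated which | Off-treatment date | Event at switch |
| Still alive | Censoring date not stated | Last assessment | Off-treatment date | Event at switch |

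Only the first PFS cell is a stated rule that credits unobserved time. The second is a gap: an analyst could use the last survival contact or the last disease assessment. Section 6.3.3 pulls the other way. Completing therapy is itself a way of going off treatment, so its sentence, taken literally, would stop the CTCL clock for TTP or DOR no later than about 6 × 28 = 168 days from the start of treatment, plus any delays. It does not say whether that date is an event or a censoring time.

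**2. Inputs for an illustration**

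The plan states no figure for PFS or DOR, so there is none to reproduce.

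- Median PFS 3.5 months (pralatrexate, 1.2.2).
- Post-switch median survival, taken as the gap between the median OS and median PFS in 1.2.2: 14.5 − 3.5 = 11 months (pralatrexate) and 7.9 − 1.6 = 6.3 months (belinostat). A difference of two medians is only a rough anchor.
- Share switching before progression, s: assumed 10 to 30%.

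**3. Formula**

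With exponential times, let λp = ln 2/3.5 = 0.198 per month, λs = λp·s/(1 − s), λd = ln 2/(post-switch median) and L = λp + λs. If switchers are followed to death,

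S(t) = e^(−Lt) + λs·[e^(−λd·t) − e^(−Lt)]/(L − λd).

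Without switching, S(12) = e^(−0.198×12) = 0.093.

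For s = 25%, λs = 0.0660 and L = 0.2641:

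- 11 months (λd = 0.0630): 0.0421 + 0.0660 × (0.4695 − 0.0421)/0.2010 = 0.182.
- 6.3 months (λd = 0.1100): 0.0421 + 0.0660 × (0.2671 − 0.0421)/0.1540 = 0.138.

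| 12-month PFS as recorded (9.3% without switching) | s = 10% | s = 25% | s = 30% |
|---|---|---|---|
| Post-switch median 6.3 months | 11% | 14% | 15% |
| Post-switch median 11 months | 13% | 18% | 20% |

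The median moves little: at s = 25% and 11 months it reads 3.86 instead of 3.50 months, and 6-month PFS reads 36% instead of 31%.

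**4. Direction**

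With a post-switch median of 2 months and s = 25%, the same formula gives S(12) = 0.063, below 0.093. Measured against the no-switch curve, early death after a switch lowers PFS.

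**5. Does censoring repair it?**

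A simulation of 300,000 patients per scenario used 8-weekly assessments, median PFS 3.5 months, a median of 6.3 months from progression to death, a switch at a uniform time before progression, and no effect of the new therapy on the progression date. The 8-week grid raises the true values slightly, to 33% at 6 months and 11% at 12.

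| s | 6-month PFS, followed to death | 6-month PFS, censored at last assessment | 6-month EFS |
|---|---|---|---|
| 10% | 38% | 35% | 31% |
| 20% | 42% | 37% | 29% |
| 30% | 47% | 39% | 27% |

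Censoring cuts the excess from about 5 to 13 points to about 2 to 6. The remainder is informative censoring, since in this set-up switches cluster ahead of progression. EFS lies below the truth, so it brackets PFS from the other side.

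**The case against.** A reader might infer that PFS and DOR are both inflated, and always upward. The documents do not support that:

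- Section 6.3.6 already ends DOR at the last assessment when there is no progression, and 6.3.3 can shorten it. The DOR fault is inconsistency and an unclear place for later deaths.
- Silence on living switchers is not a rule that inflates PFS. Censoring them at the last disease assessment fits 6.3.7 equally well.
- Step 4 shows that the direction depends on survival after the switch.

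Other points stand in part. The illustration rests on an assumed switching rate, and 11 months is the longest OS-to-PFS gap in 1.2.2. For 27 patients the approximate 95% half-width around 9.3% is 1.96 × √(0.093 × 0.907/27) = 11 points, wider than the 9-point shift at 25% switching and 11 months. That limits the practical weight of the shift but does not excuse an undefined rule.

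Telephone and CBC-only contacts are fallbacks, since imaging is scheduled at follow-up visits for up to 3 years. They matter here only because 6.3.6 does not define an assessment. EFS is already planned with PFS and DOR. It gives a comparison but does not supply the missing PFS rule.

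**Conclusion.** The point holds in a limited form. Read literally, the plan dates the PFS event at death for a patient who switches without progression and then dies, after a period with no scheduled search for progression. For living switchers the PFS censoring date is missing. For DOR, 6.3.6 and 6.3.3 conflict, and post-switch death is unresolved.

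The size is illustrative only: 2 to 6 points on 12-month PFS at a post-switch median of 6.3 months, and 3 to 11 points at 11 months, for 10 to 30% switching. This assumes exponential times, switching unrelated to prognosis and every switcher followed to death. MTD and adverse-event endpoints are unaffected, and no hypothesis test depends on PFS or DOR. The rule should still be settled before analysis.

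**What to change.** 1. In 6.3.6, 6.3.7 and 10.4.3, state that if new anti-lymphoma therapy starts without progression, PFS and DOR are censored at the last disease assessment before it, and that later deaths are not PFS or DOR events.
2. Define a disease assessment as imaging, mSWAT or blood disease evaluation. Telephone, email and CBC-only contacts do not count.
3. Reconcile the off-treatment-date sentence in 6.3.3 with 6.3.6, so that one rule governs DOR in each disease group and TTP in CTCL.
4. Report how many patients switched before progression, and present the planned EFS as the sensitivity analysis for informative switching.

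**Cost.** Wording only, because 3.5.4 already collects new treatments. There will be fewer PFS and DOR events, hence wider intervals, and some bias from informative censoring will remain. The switcher count and EFS let the reader judge it.

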6.3.8 Overall Survival

Overall survival (OS) is defined as the time from the date of study enrollment until time of death from any cause.

6.3.9 Event-Free Survival

Event-free survival (EFS) is defined as the duration of time from the date of study enrollment until time of disease relapse, disease progression, alternative therapy for lymphoma given (such as radiation), or death, whichever occurs first.

6.4 TOXICITY CRITERIA

The following adverse event management guidelines are intended to ensure the safety of each patient while on the study. The descriptions and grading scales found in the revised NCI Common

Terminology Criteria for Adverse Events (CTCAE) version 5.0 will be utilized for AE reporting. All appropriate treatment areas should have access to a copy of the CTCAE version 5.0. A copy of the CTCAE version 5.0 can be downloaded from the CTEP web site (http://ctep.cancer.gov/protocolDevelopment/electronic_applications/ctc.htm).

7 NIH REPORTING REQUIREMENTS/DATA AND SAFETY MONITORING PLAN

7.1 DEFINITIONS

Please refer to definitions provided in Policy 801: Reporting Research Events found [here](#).

7.2 OHSRP OFFICE OF COMPLIANCE AND TRAINING/ IRB REPORTING

7.2.1 Expedited Reporting

Please refer to the reporting requirements in Policy 801: Reporting Research Events and Policy 802 Non-Compliance Human Subjects Research found [here](#). Note: Only IND Safety Reports that meet the definition of an unanticipated problem will need to be reported per these policies.

7.2.2 IRB Requirements for PI Reporting at Continuing Review

Please refer to the reporting requirements in Policy 801: Reporting Research Events found [here](#).

7.3 NCI CLINICAL DIRECTOR REPORTING

Problems expeditiously reported to the OHSRP in iRIS will also be reported to the NCI Clinical Director. A separate submission is not necessary as reports in iRIS will be available to the Clinical Director.

In addition to those reports, all deaths that occur within 30 days after receiving a research intervention should be reported via email to the Clinical Director unless they are due to progressive disease.

To report these deaths, please send an email describing the circumstances of the death to [name] at [contact] within one business day of learning of the death.

7.4 NIH REQUIRED DATA AND SAFETY MONITORING PLAN

7.4.1 Principal Investigator/Research Team

The clinical research team will meet at least weekly when patients are being actively treated on the trial to discuss each patient. Decisions about dose level enrollment and dose escalation if applicable will be made based on the toxicity data from prior patients.

All data will be collected in a timely manner and reviewed by the principal investigator or a lead associate investigator. Events meeting requirements for expedited reporting as described in section [7.2.1](#) will be submitted within the appropriate timelines.

The principal investigator will review adverse event and response data on each patient to ensure safety and data accuracy. The principal investigator will personally conduct or supervise the investigation and provide appropriate delegation of responsibilities to other members of the research staff.

8 SPONSOR SAFETY REPORTING

8.1 DEFINITIONS

8.1.1 Adverse Event

Any untoward medical occurrence in a patient or clinical investigation subject administered a pharmaceutical product and which does not necessarily have a causal relationship with this treatment. An adverse event (AE) can therefore be any unfavorable and unintended sign (including an abnormal laboratory finding), symptom, or disease temporally associated with the use of a medicinal (investigational) product, whether or not related to the medicinal (investigational) product (ICH E6 (R2)).

8.1.2 Serious Adverse Event

An adverse event or suspected adverse reaction is considered serious if in the view of the investigator or the sponsor, it results in any of the following:

- Death,
- A life-threatening adverse event (see **8.1.3**)
- Inpatient hospitalization or prolongation of existing hospitalization
 - A hospitalization/admission that is pre-planned (i.e., elective or scheduled surgery arranged prior to the start of the study), a planned hospitalization for pre-existing condition, or a procedure required by the protocol, without a serious deterioration in health, is not considered a serious adverse event.
 - A hospitalization/admission that is solely driven by non-medical reasons (e.g., hospitalization for patient or subject convenience) is not considered a serious adverse event.
 - Emergency room visits or stays in observation units that do not result in admission to the hospital would not be considered a serious adverse event. The reason for seeking medical care should be evaluated for meeting one of the other serious criteria.
- Persistent or significant incapacity or substantial disruption of the ability to conduct normal life functions
- A congenital anomaly/birth defect.
- Important medical events that may not result in death, be life-threatening, or require hospitalization may be considered a serious adverse drug experience when, based upon appropriate medical judgment, they may jeopardize the patient or subject and may require medical or surgical intervention to prevent one of the outcomes listed in this definition.

8.1.3 Life-threatening

An adverse event or suspected adverse reaction is considered "life-threatening" if, in the view of either the investigator or sponsor, its occurrence places the patient or subject at immediate risk of death. It does not include an adverse event or suspected adverse reaction that, had it occurred in a more severe form, might have caused death. (21CFR312.32).

8.1.4 Severity

The severity of each Adverse Event will be assessed utilizing the CTCAE version 5.

8.1.5 Relationship to Study Product

All AEs will have their relationship to study product assessed using the terms: related or not related.

- Related – There is a reasonable possibility that the study product caused the adverse event. Reasonable possibility means that there is evidence to suggest a causal relationship between the study product and the adverse event.
- Not Related – There is not a reasonable possibility that the administration of the study product caused the event.

8.2 ASSESSMENT OF SAFETY EVENTS

AE information collected will include event description, date of onset, assessment of severity and relationship to study product and alternate etiology (if not related to study product), date of resolution of the event, seriousness and outcome. The assessment of severity and relationship to the study product will be done only by those with the training and authority to make a diagnosis and listed on the Form FDA 1572 as the site principal investigator or sub-investigator. AEs occurring during the collection and reporting period will be documented appropriately regardless of relationship. AEs will be followed through resolution.

SAEs will be:

- Assessed for severity and relationship to study product and alternate etiology (if not related to study product) by a licensed study physician listed on the Form FDA 1572 as the site principal investigator or sub-investigator.
- Recorded on the appropriate SAE report form, the medical record and captured in the clinical database.
- Followed through resolution by a licensed study physician listed on the Form FDA 1572 as the site principal investigator or sub-investigator.

For timeframe of recording adverse events, please refer to section [6.1](#). All serious adverse events recorded from the time of first investigational product administration must be reported to the sponsor with the exception of any listed in section [8.4](#).

8.3 REPORTING OF SERIOUS ADVERSE EVENTS

Any AE that meets protocol-defined serious criteria or meets the definition of Adverse Event of Special Interest that require expedited reporting must be submitted immediately (within 24 hours of awareness) to OSRO Safety using the CCR SAE report form. Any exceptions to the expedited reporting requirements are found in section [8.4](#).

All SAE reporting must include the elements described in section [8.2](#).

SAE reports will be submitted to the Center for Cancer Research (CCR) at: [contact] and to the CCR PI and study coordinator. CCR SAE report form and instructions can be found at:

<https://ccrod.cancer.gov/confluence/display/CCRCRO/Forms+and+Instructions>

Following the assessment of the SAE by OSRO, other supporting documentation of the event may be requested by the OSRO Safety and should be provided as soon as possible.

8.4 WAIVER OF EXPEDITED REPORTING TO CCR

As death due to disease progression is part of the study objectives, and captured as an endpoint in this study, it will not be reported in expedited manner to the sponsor. However, if there is evidence suggesting a causal relationship between the study drug and the event, report the event in an expedited manner according to section **8.3**.

